### **9.3 Subject Lost to Follow-Up**

In the event that all possible attempts to locate the subject for the Day 21 follow up interview have failed, all efforts made by the site study personnel to contact the subject will be documented and included in the subject's study binder.

## **10 SAFETY AND ADVERSE EVENTS**

### **10.1 Safety Sub-study**

The safety of the MBT has been demonstrated in several clinical applications. However, the repeated administration of the test substrate, which represents the equivalent of 75 mg of APAP per administration, will be closely monitored to ensure that this small dose of APAP will not result in additional liver injury (particularly in the presence of NAC). The results of the Retrospective Safety Study were examined before enrollment in the prognosis study began, as outlined in Section 4.2.3 of this protocol. A second, prospective safety study will be performed and sera collected from the first 20 ALF subjects enrolled into the ALF-MBT Trial as described herein, in whom we propose to administer MBT on Day 2, 3, 5, and 7 unless the subject is discharged/transferred, transplanted or dies. Serum for acetaminophen (APAP) and APAP-adduct levels will be collected with routine AM labs on each day from Day 2-7, as well as Day 1 as a baseline value. Serum samples will be reserved for the sole purpose of determining APAP or APAP-adducts levels in patients with ALF during repeated administrations of the C-Methacetin solution and will be performed by [name] at the University of Arkansas for Medical Sciences, Little Rock, AR.

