
Study Procedures Continued
	
administered during dialysis treatments and subjects remain fasting for the duration of the breath test collection.
 
Consumption of the following drugs that may interfere with (compete with or induce) the metabolism of C-Methacetin will be recorded on the case report forms and include the following:
 
 
a. HMG-CoA reductase (Statin) drugs in the 30 days prior to study enrollment;
 
b. Acyclovir and famotidine taken in the 48 hours prior to study enrollment; and
 
c. Any of the following taken during the study period: allopurinol, carbamazepine, cimetidine, ciprofloxacin, daidzein, disulfiram, Echinacea, enoxacin, fluvoxamine, methoxsalen, mexilitene, montelukast, norfloxacin, phenylpropanolamine, phenytoin, propafenone, rifampin, terbinafine, ticlodipine, thiabendazole, verapamil, zileuton or oral contraceptives.
 

Safety Evaluations
	
This is not a therapy trial; however, the safety of administration of C-Methacetin solution in this setting will be evaluated. Safety assessments will be performed by assessing for acetaminophen levels and levels of acetaminophen-Cys adducts, by collecting daily serum samples for adduct and APAP testing in the laboratory of [name], University of Arkansas for Medical Sciences, Little Rock, AR, on the first 20 evaluable ALF patients.

Safety Analysis
	
The detection of serum APAP-Cys adducts in those ALF patients not thought secondary to APAP toxicity will be considered significant if a value > 1.0 nmol/L is determined. Likewise, the detection of any level serum APAP in these patients will also be considered significant. An increase of significance in the adduct level in APAP cases or in serial serum APAP levels will also require adjudication as a possible indicator of an additional adverse effect of C-Methacetin administration. In addition, standard laboratory parameters including serum electrolytes and Liver biochemistries will be measured in all subjects through a maximum of 7 days (See Schedule of Assessments, Section 8.5).

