### 4.2.3 Safety Endpoints

The administration of Methacetin (75mg/dose) results in the generation of acetaminophen (75mg/dose), and therefore presents a modest safety concern in patients with ALF, particularly in those with APAP overdose. Use of NAC in patients admitted with APAP overdose or non-APAP ALF should obviate minor adverse effect potential of this small dose. In a retrospective study, sera from ALF patients who were given the C-Methacetin MBT at King's College were assayed for presence of acetaminophen adducts. Participants of this study received MBT daily up to 7 days. No *de novo* appearance of adducts was observed for non-APAP subjects, nor was there an increase in adduct levels in acetaminophen toxicity subjects.

To confirm the safety profile of the MBT, a prospective safety sub-study is planned for this protocol as outlined in Section 10.1. This safety sub-study will include determining APAP and APAP-adduct concentrations in sera from study participants with ALF immediately prior to each administration of the C-Methacetin solution. A positive safety endpoint is defined as:

1. the absence of decline in APAP or APAP-adduct concentration between two consecutive determinations for patients with ALF due to APAP overdose;
2. presence of a significant (toxic quantity,  $\geq 1 \mu\text{mol/L}$ ) APAP-adducts in patients with non-APAP ALF;
3. adjudicated cases where APAP (non-adduct, parent compound) is detected in the serum of a patient with non-APAP ALF. It should be noted that in some instances, APAP appears to be detected in patients with non-APAP ALF if the total bilirubin is  $\geq 10 \text{ mg/dl}$ ; these are considered false-positive due to the cross-reactivity between APAP reactants and bilirubin in some colorimetric APAP assays (Polson, et al.). Such cases of detectable APAP in patients with non-APAP ALF will be adjudicated on an individual basis by the study's appointed

independent Medical Safety Monitor to determine the likelihood of Methacetin toxicity. Results of adduct testing will initially be reviewed internally and forwarded in real time to the MSM for review. These data will then be reported in summary fashion to the DSMB.

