#### **8.3 Performance of the APAP Adduct Assays and APAP Concentration Assays**

Serum for acetaminophen (APAP) and APAP-adduct levels will be collected with routine morning labs on each day from Day 2-7, as well as Day 1 as a baseline value, from the first 20 ALF subjects enrolled. Serum samples will be reserved for the sole purpose of determining whether APAP or APAP-adducts accumulate during repeated administrations of the C-Methacetin solution in patients with ALF. The collected samples will be shipped to and analyzed by [name] at the University of Arkansas.

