#### **8.4 Clinical and Laboratory Assessments**

Subjects will routinely undergo laboratory tests as part of the ALFSG Registry. Specific to this study, sites will be required to collect lactate, ammonia, phosphate, AST/ALT, creatinine, bilirubin and INR on a daily basis.

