## 8.5 Schedule of Assessments

	Screening/ Subject Enrollment	Day 1	Day 2	Day 3	Day 5	Day 7	Day 21
Demographics	X						
Medical History	X						
Confirm Eligibility Criteria ^	X						
Prior Medications	X						
Concomitant Medications		X	X	X	X	X	
Grade of HE	X	X	X	X	X	X	
Labs (lactate, bicarbonate, INR, total bilirubin, phosphate, Creatinine, WBC, Platelet count, ammonia-arterial or venous (if clinically indicated))		X	X	X	X	X	
RRT (record time/tx prior to MBT)		X	X	X	X	X	
MBT		X	X	X	X	X	
Serum for APAP and APAP-adduct levels*		X	X	X	X	X	
AE Reporting		X	X	X	X	X	(SAEs only)
End of Study							X
Collection of data for MELD, KCC, and ALFSG- PI	X	X	X	X	X	X	

\* Only in the first 20 consecutive ALF subjects enrolled

^ In women of child-bearing potential; Urine pregnancy test or blood human chorionic gonadotropin (hCG) is acceptable.

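### The 8.5 schedule omits the Day 4 and Day 6 APAP and adduct serum draws that 8.3 and 10.1 require; a site following the grid would lose two safety samples per subject

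*Combined protocol and SAP*

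**What the plan says.** Three places call for daily serum in the safety sub-study:

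- Section 10.1: serum "will be collected with routine AM labs on each day from Day 2-7, as well as Day 1 as a baseline value".
- Section 8.3: serum "will be collected with routine morning labs on each day from Day 2-7, as well as Day 1 as a baseline value". It gives the sole purpose as "determining whether APAP or APAP-adducts accumulate during repeated administrations of the" test solution.
- Synopsis, Safety Evaluations: safety is assessed "by collecting daily serum samples for adduct and APAP testing". No day range is given there.

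The 8.5 schedule has columns for Days 1, 2, 3, 5, 7 and 21. Its row "Serum for APAP and APAP-adduct levels" is marked on Days 1, 2, 3, 5 and 7, with a footnote limiting it to the first 20 consecutive ALF subjects.

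Section 4.2.3 says the sub-study will include measuring concentrations "in sera from study participants with ALF immediately prior to each administration of the" solution, and refers to 10.1 for the outline. It defines three positive safety endpoints. The first is "the absence of decline in APAP or APAP-adduct concentration between two consecutive determinations for patients with ALF due to APAP overdose". The second and third concern toxic adduct levels and detectable parent APAP in non-APAP ALF.

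Doses are given with the breath tests on Days 1, 2, 3, 5 and 7 (8.2).

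**The concern.** Coordinators tend to work from the schedule of assessments, and here it gives fewer serum draws than the text that defines the sub-study. A sample not taken on Day 4 or Day 6 cannot be recovered later.

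The two days matter because the first endpoint compares consecutive determinations, so the draw days decide what is compared. Without Days 4 and 6, the 24 h after the Day 3 dose is merged with the dose-free 24 h that follows, and likewise after the Day 5 dose. A level that holds or rises after the dose and then falls would be recorded only as a net fall. The other two endpoints simply get fewer looks.

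**Working it through.** The documents give no sample-size or power figure for the sub-study, so there is nothing to reproduce. The check is a count, an ordering argument and an illustration.

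**Inputs.** Dose days 1, 2, 3, 5, 7 (8.2). Draw days 1 to 7 (8.3, 10.1) or 1, 2, 3, 5, 7 (8.5). Up to 20 ALF subjects (8.5 footnote). Each dose-day draw comes before the dose, as 8.2.1 requires for protocol-specified labs. Intervals are approximate, since serum goes with morning labs and each breath test is timed to match the first.

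**Count, per subject completing all five tests.**

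| | Daily (8.3, 10.1) | 8.5 grid |
|---|---|---|
| Draws | 7 | 5 |
| Consecutive pairs | 6, all 24 h | 4: two 24 h, two 48 h |
| Doses with a next-day sample | 4 of 5 (Days 1, 2, 3, 5) | 2 of 5 (Days 1, 2) |
| Samples after the first dose | 6 | 4 |
| Maximum draws, 20 subjects | 7 × 20 = 140 | 5 × 20 = 100 |

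The four daily pairs 3–4, 4–5, 5–6 and 6–7 collapse into 3–5 and 5–7. Pairs 3–4 and 5–6 each contain a dose; 4–5 and 6–7 do not. The totals are maxima, because discharge, transfer, transplant or death ends testing early.

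**Direction of the effect on the first endpoint.** Let a and b be the log changes over the two halves of a 48 h gap. The grid flags non-decline if a + b ≥ 0; daily draws flag it if a ≥ 0 or b ≥ 0. If both a and b are negative, so is a + b. Hence every non-decline seen on five draws is also seen on seven, but not the reverse. Example with assumed values: +5% from Day 3 to 4 and −20% from Day 4 to 5 give 1.05 × 0.80 = 0.84, a net 16% fall. Daily draws meet the endpoint; the grid does not.

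**Size, under assumptions only.** With first-order decay, half-life h and one dose raising the level at once, no decline over t hours needs increment ÷ pre-dose level ≥ 2^(t/h) − 1:

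| Assumed half-life | 24 h pair | 48 h pair |
|---|---|---|
| 24 h | 1.00 | 3.00 |
| 36 h | 0.59 | 1.52 |
| 48 h | 0.41 | 1.00 |
| 72 h | 0.26 | 0.59 |

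A simulation (200,000 subjects per scenario, assay CV 10%, increment per dose as a fraction of the Day 1 level) gave these percentages with at least one non-declining pair, daily against grid:

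| Half-life | Increment 0 | 0.1 | 0.2 | 0.4 |
|---|---|---|---|---|
| 24 h | 0.0 v 0.0 | 41.8 v 0.0 | 86.5 v 0.2 | 98.5 v 5.2 |
| 36 h | 0.3 v 0.1 | 24.8 v 1.5 | 64.9 v 7.8 | 95.2 v 44.9 |
| 48 h | 4.3 v 1.5 | 38.0 v 9.4 | 75.9 v 29.8 | 98.9 v 82.1 |

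No scenario had a subject flagged on the grid but not on daily draws. With a non-zero increment the difference runs from 98.9 − 82.1 = 16.8 to 98.5 − 5.2 = 93.3 percentage points. The inputs are not in the documents, so the range shows only that the size cannot be fixed from them.

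**The case against.** The strongest reply is that this is a layout matter. The grid lists breath-test days and omits Days 4 and 6 for every row, including items the text requires throughout: 8.4 says "sites will be required to collect lactate, ammonia, phosphate, AST/ALT, creatinine, bilirubin and INR on a daily basis", and 10.2 records adverse events from Day 1 through Day 7. Nobody would conclude that adverse events go unrecorded on Day 4. This stands as an explanation. It does not make the table right: three sections state a daily requirement and the operational table does not show it.

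A reader might infer more than the documents support:

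- *That 4.2.3 independently sets a five-draw design, with nothing to say which section prevails.* Section 4.2.3 says the sub-study will include pre-dose measurements, which is not exclusive, and it defers to 10.1. Daily draws taken before any dose that day satisfy both.
- *That data from sites following different sections could not be pooled.* Days 1, 2, 3, 5 and 7 are common to both readings, so pooling is possible at the price of discarding Days 4 and 6.
- *That the masking problem reaches all 20 subjects.* The non-decline endpoint covers only ALF due to APAP overdose, and the documents do not say how many of the 20 that will be.
- *That every additional flag is a gain.* More pairs also give more chance non-declines: 4.3% against 1.5% with no increment, a 48 h half-life and a 10% CV.

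In addition, 4.2.3 reports a retrospective study, with tests daily for up to 7 days, that found no new adducts in non-APAP subjects and no increase in APAP subjects. This lowers the expected risk but does not remove the reason for the prospective samples.

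**Conclusion.** The 8.5 serum row is wrong as written and should be corrected. If a site follows it, each subject completing all five tests has 5 samples instead of 7. The Day 3 and Day 5 doses lose their next-day sample but keep one at about 48 h, and the adduct and APAP detection endpoints get 4 looks after the first dose instead of 6. For APAP-overdose subjects only, the two merged gaps can hide a failure to decline.

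The counts and the direction rest only on the stated dose and draw days and on drawing before dosing. How much detection is lost is unknown. The loss occurs only where a site follows the grid over 8.3, 10.1 and the synopsis. The Day 7 dose has no later serum sample under either reading; that is a design choice and not part of this inconsistency. The reach is the 20-subject safety sub-study.

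**What to change.** In 8.5, add Day 4 and Day 6 to the serum row, either as columns or as a footnote to the effect of: *daily on Days 1–7, per 8.3 and 10.1; drawn before any dose that day*.

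As an optional clarification, reword 4.2.3 so that serum is taken daily on Days 1–7, before any dose on that day. There is no need to fix consecutive determinations at 24 h, which would leave the pair around a missed draw undefined.

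Cost: at most 2 × 20 = 40 draws relative to the grid, all already required by 8.3 and 10.1 and taken with routine morning labs. No extra subjects or breath tests are needed. The accepted downside is a somewhat higher chance of a spurious non-decline.

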### **10.2 Adverse Events**

Adverse event reporting and procedures are described in detail in the MOP.

In the ALFSG-MBT Trial, any medical conditions not present prior to the initial administration of the test substrate but that emerge after the initial test substrate is administered are considered AEs. Adverse Events encountered from Day 1 through Day 7 of the study period will be recorded, and Serious Adverse Events from Day 1 through the Day 21 of the study period will be recorded.

Designated study personnel at all investigative sites are responsible for entering any and all non-serious and serious adverse events, regardless of severity or relationship to the C-Methacetin solution and device, and including updates to adverse event information (e.g., date of resolution, action taken) as needed, into the WebDCU™ database within timelines defined in the MOP and in the subject's source documents. Upon data submission of the SAE eCRF, the system will trigger an automatic e-mail notification to the independent Medical Safety Monitor (MSM) stating that an SAE has occurred. The MSM will access the information via the password protected web based system for review and report safety concerns to the DSMB.

Adverse events will be defined and severity graded according to the Common Terminology Criteria for Adverse Events (CTCAE) found in the MOP. AEs will be submitted online through WebDCU™ and coded centrally into standard terminology using AEs will be using the Medical Dictionary for Regulatory Activities (MedDRA). Guidelines for report content and structure are provided in the MOP.

### **10.3 Data Safety Monitoring Board (DSMB)**

The Data Safety Monitoring Board (DSMB) used for this study will be that designated by NIDDK to oversee the ALFSG. Semi-annual data quality and safety reports will be provided to the DSMB. This timeline can be changed by the DSMB if requested. The analysis of all adverse events will include incidence tables and summary of AEs and SAEs by severity and relationship to device or drug.

## **11 DATA MANAGEMENT**

### **11.1 Data Handling**

The raw data from the individual tests on the BreathID® MCS device will be analyzed using Exalenz's trending software. This program provided by Exalenz will combine all tests for any given subject bearing the same identification number and will plot the trend of the breath test results with the percent change displayed. This analysis will be carried out only after the subject has completed his/her participation in the study and in order not to bias the treating physician, the results will not be shared until the study is completed.

For all other study data, sites will enter case report form data into the password protected study database housed in WebDCU™. The WebDCU™ is a validated web-based clinical trials

management system that provides the infrastructure for real-time data capture and data sharing and includes designated web servers and supporting database servers. This user-friendly web-based database system will be used for subject enrollment, data entry, data validation, project progress monitoring, user customizable report generation, and secure data transfer. The web-based data capturing system allows for study data to be directly entered into the study specific database by the site via a secure internet connection. Secure Socket Layer (SSL) is used for data encryption. The web system combines all study tools into one system which includes study database, online training and help desk, subject calendar, electronic data clarification request (DCR) process, data entry, case report form (CRF) and participate tracking system, audit trail, and report generation mechanisms. This is the system used for the currently ongoing ALFSG Registry. Clinical and laboratory data will be collected by the site in order to derive MELD, ALFSG-PI, ALI-PI and KCC scores on a daily basis. These clinical data and laboratories are mandatory as they will be needed for calculation of the clinical outcome predictor indices.

## **12 STATISTICAL CONSIDERATIONS**

### **12.1 Sample Size**

The relationship between the Day 1 PDRPeak and clinical outcome (21-day spontaneous survival) will be assessed using logistic regression with a two-sided alpha of 0.10. Based on previous enrollment rates from the ALFSG Registry, we estimate an accrual rate of approximately 100 ALF or non-APAP ALI patients per year into the ALFSG-MBT Trial. The power of the logistic model predicting ‘good’ outcome (21 Day SS) is based on the proportion of ‘good’ outcome at the mean MBT value. Assuming this proportion is 0.50, we determined that approximately 200 enrolled non-APAP ALI and ALF patients are needed in order to ensure sufficient power (80%) to detect odds ratios of 1.5 or higher.

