### **3.2 Summary of BreathID® and MBT Clinical Data**

The BreathID® MBT has been used to assess the functional capacity of the liver in several clinical situations. In a study of 165 patients with cirrhosis which included two ALFSG sites, MBT predicted liver-related death and the appearance/exacerbation of ascites better than the Model for End-Stage Liver Disease (MELD) score (6, copy attached).

MBT has also been used in a pilot study of patients with ALF performed at Kings College Hospital and in Israel (7). Sixty-two patients with severe ALI/ALF of diverse etiologies were followed with the MBT during the acute phase of their illness. During their hospital course, 62% of patients spontaneously survived, 21% underwent liver transplantation, and 18% died with a mean follow-up of 7 days after baseline testing. In patients who spontaneously recovered, admission PDR and CPDR at 20 minutes after Methacetin ingestion were higher than those who died or underwent liver transplantation, with p-value of approximately 0.08 for the difference for both indices. Moreover, in the 38 patients in whom post-admission MBTs were available, PDR20 and CPDR20 were both much higher in spontaneous survivors (SS) than those who died or underwent transplant (p=0.0002 and 0.001, respectively), as were the changes in both parameters between Day 1 and Day 2-4. (The choice of the later day was not standardized. Values were used in the following order of preference depending upon their availability: Day 3, Day 4, or Day 2, if neither Day 3 nor 4 were available). Subgroup analyses clearly showed that patients who died or underwent transplant had similar PDR20 and CPDR20 on Day 1, but both were significantly lower than SS. These data strongly support the hypothesis that the MBT may assess the severity of ALF at

admission and the likelihood of hepatic recovery within 7 days of admission more accurately than laboratory tests regardless of the etiology of liver injury.

**Table 1. Methacetin breath test (MBT) results in 62 patients with ALI/ALF on admission (Day 1) and in 38 patients at one time point after admission (Day 3, or Day 2 or 4 if Day 3 is missing).**

MBT Parameter	Day	N	Total Population	Spontaneous Survivors	Death/ Transplant	P*
			Mean±SD/ Median[range]	Mean±SD/ Median[range]	Mean±SD/ Median[range]	
PDR 20	1	62	2.60[-1.71 - 33.02]	3.31[-1.71 - 13.52]	1.13[-1.22 - 12.80]	0.088

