### **5.2 Study Population**

Up to 200 evaluable male and female patients, aged 18 to 80 years (have not reached their 81st birthday) with severe acute liver injury not related to acetaminophen overdose or acute liver failure present at the time of enrollment into the ALFSG Registry will be consecutively enrolled. An evaluable patient is one who has completed one or more Breath Tests measured for a minimum of 30 (and ideally 60) minutes after administration of the C-Methacetin solution.

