#### **8.2.4 Interruptions and Confounders of the Breath Test**

Breath Tests should be timed to anticipate interruptions and possible confounders. Recognizing that patients with ALI and ALF are critically ill, guidelines if deviations occur can be found in the ALFSG-MBT Manual of Procedures.

Should an interruption in breath collection due to removal of the cannula or its disconnection occur during the administration of the MBT and the device cannot compute the delta over baseline (DOB) results, the next MBT will not be repeated until 24-hours after the interruption time of the previous Breath Test. If the interruption occurred at the beginning of the Breath Test (during baseline breath collection) and before ingestion of the C-Methacetin solution, the test can be repeated immediately. If the interruption occurs on Days 3 or 5, then the study team should perform the MBT on the next study day as outlined in the Schedule of Assessments. The MBT is considered ‘performed’ and the subject “evaluable” if it has been measuring the subject’s breath for a minimum of 30 (and preferably 60) minutes after test substrate has been administered.

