### **12.2.2 Final Analyses**

Preliminary analyses will be conducted to describe the collected variables. Univariate descriptive statistics and frequency distributions will be calculated, as appropriate for all collected variables along with two-sided 95% confidence intervals. The primary endpoint, Day 1 PDRPeak will be compared between those that spontaneously survive (SS) by Day 21 and those that either die or receive a transplant by Day 21 with a logistic regression model at a two-sided alpha level of 0.10. All enrolled patients with a value at Day 1 will be included in the analysis. The primary analysis will not stratify by non-APAP ALI/ALF but exploratory analyses will be conducted that examine potential differences as described below. It is not anticipated that any enrolled patient will be missing the outcome of SS.

There are several exploratory aims that will be conducted for future hypothesis generation. In addition to the comparison of mean PDRPeak values between the two cohorts, a cutpoint for the PDRPeak value will be examined using a receiver operating curve. The identified cutpoint will be compared to other known prognostic indices including Kings College criteria (KCC), Model of End-Stage Liver Disease (MELD), and the ALFSG-PI (prognostic index). As a secondary analysis and where serial measurements are available, the trends in the MBT results (PDRPeak, PDR20, CPDR20) will be related to outcome (Day 21 SS) using repeated measures analysis. A multivariable regression will be performed to assess if PDRPeak, in combination with traditional prognostic measures provides an accurate prediction of Day 21 outcome. These pre-specified exploratory analyses will be conducted using a significance level of 0.05.

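### Does the sample size of about 200 in Section 12.1 contradict its own alpha, power and odds ratio?

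*Combined protocol and SAP*

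**What the plan says.** Section 12.1 states that the relation between Day 1 PDRPeak and Day 21 spontaneous survival "will be assessed using logistic regression with a two-sided alpha of 0.10". The power calculation is anchored on the proportion of good outcomes at the mean marker value: "Assuming this proportion is 0.50". It concludes that "we determined that approximately 200 enrolled non-APAP ALI and ALF patients are needed in order to ensure sufficient power (80%) to detect odds ratios"; the smallest odds ratio it names is 1.5. It names no unit for the odds ratio, no SD or distribution for PDRPeak, no formula, and no allowance for patients without a usable Day 1 test.

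Three counts appear in the document. Section 12.1 speaks of enrolled patients. Section 5.2 plans up to 200 evaluable patients and defines the term by any test: "An evaluable patient is one who has completed one or more Breath Tests measured for a minimum of 30 (and ideally 60) minutes". Section 12.2.2 sets the primary analysis population: "All enrolled patients with a value at Day 1 will be included in the analysis".

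**The concern.** A reader who puts the four stated inputs into a standard formula, taking the odds ratio per 1 SD, gets a number well below 200. The section then seems to misstate either the sample size or the power, and it is the plan's only statement of what the trial can detect.

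The three counts add to the doubt. Under Section 8.2.4, if a test is interrupted after dosing and no result can be computed, "the next MBT will not be repeated until 24-hours after the interruption time of the previous Breath Test". A patient whose Day 1 test fails this way can become evaluable on Day 2 and still be absent from the primary analysis. If 200 had been calculated as the number to analyse, with no margin, such losses would take the trial below its stated power, and Section 12.1 would not show it.

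**Working it through.** **Inputs from Section 12.1.** Two-sided alpha 0.10 (z = 1.645), power 80% (z = 0.842), odds ratio 1.5 (ln 1.5 = 0.4055, squared 0.1644), proportion p = 0.50 at the mean. **Assumed, not in the document:** the odds ratio is per 1 SD of a normally distributed marker.

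**Analysed patients needed for 80% power**

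- Hsieh 1998: N = (1.645 + 0.842)² / [p(1 − p)(ln OR)²] = 6.183 / (0.25 × 0.1644) = 150.4, so 151.
- Whittemore/Hsieh 1989, which adds a correction for the spread of the marker: 163.9, so 164.
- Wald test with the information expected under the alternative: the variance factor is 4.488 in place of 4, so N = 6.183 × 4.488 / 0.1644 = 168.8, so 169.
- Simulation of the Wald and likelihood-ratio tests reaches 80% at about 157-160.

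**Power with 200 analysed**

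- Hsieh 1998: Φ(√(200 × 0.25) × 0.4055 − 1.645) = Φ(1.222) = 88.9%.
- Hsieh 1989: 86.6%.
- Expected-information Wald: Φ(√(200 / 4.488) × 0.4055 − 1.645) = Φ(1.062) = 85.6%.
- Simulation: about 87%, or 86% if the futility stop in Section 12.2.1 is always followed.

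With 180 analysed (10% of 200 lost), the formulas give 86%, 83% and 82%, and simulation gives 84%.

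**What would reproduce 200.** Each of these is sufficient alone, and the document confirms none of them.

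- *Loss of Day 1 values.* 1 − 151/200 = 24.5%; 1 − 164/200 = 18.0%; 1 − 169/200 = 15.5%.
- *A different step.* An odds ratio of 1.5 over 1.153 SD is 0.4055 / 1.153 = 0.3517 per SD on the log scale, and 6.183 / (0.25 × 0.3517²) = 200. The other two formulas need steps of 1.115 and 1.099 SD.
- *A calculation at two-sided alpha 0.05.* The three formulas give 191, 209 and 214, and simulated power at 200 is 79-80%. Sections 12.1 and 12.2.2 both state 0.10, so this is only a possible origin of the figure.

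**What does not explain it.** Section 3.2 reports of the pilot: "During their hospital course, 62% of patients spontaneously survived". With p = 0.62 the formulas give 160, 187 and 177, still under 200. The futility rule costs only about one point of power.

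**Marker shape.** For illustrative lognormal markers with log-SD 0.40, 0.60 and 0.85, simulated Wald power is 86%, 84% and 78% at 200 analysed, and 83%, 80% and 74% at 180. At log-SD 1.0 it is 73% by the Wald test and 78% by the likelihood-ratio test at 200. These shapes were chosen, not estimated. Table 1 in Section 3.2 cannot fix the skew: it reports PDR20, not PDRPeak, and its printed overall Day 1 maximum of 33.02 exceeds the maxima of both outcome groups (13.52 and 12.80).

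**The case for a change.** The best case for a change is that Section 12.1 cannot be reproduced as written. An odds ratio for a continuous marker has no meaning without a unit, and the usual unit misses 200 by 15.5-24.5%, which is more than rounding or choice of formula. The mismatch between enrolled, evaluable and Day 1 counts needs no assumption at all. The margin is not guaranteed either, since strong skew or heavy Day 1 loss would use it up. The remedy would be a few sentences.

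Much of this stands as description. The section does omit its unit, method and loss allowance, and the three counts do differ. What does not stand is the step from an irreproducible figure to a wrong one. The 151-169 depend on an input supplied by the reader, and they count analysed patients where Section 12.1 counts enrolled ones. Sections 8.2.1 to 8.2.4 list ordinary ways to lose a Day 1 test, including vomiting, disconnection, device failure and incomplete ingestion, so some excess of enrolled over analysed patients is to be expected.

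The suggested repairs would also put guesses into the protocol. Defining the odds ratio per 1 SD would write in a reader's assumption, and a power range for skewed markers would reflect whichever lognormals and test were chosen.

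**Conclusion.** The concern does not call for a change. On the usual reading, 200 is conservative: about 86-89% power if all 200 are analysed and about 82-86% if 180 are, against a stated 80%. On other plausible readings it is about right. The shortfall cases, 78% at 200 and 74% at 180, need marked right skew (log-SD 0.85), with extra Day 1 loss in the second. Heavier skew would lower the figure further, but the documents cannot establish how skewed PDRPeak is. All these figures assume an odds ratio per 1 SD; the main ones also assume a near-normal marker and a proportion of 0.50 at its mean.

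The missing detail does not affect the conduct or result of the trial. Section 12.2.2 already fixes the model, the alpha and the primary population, so a patient with no Day 1 value is out of that analysis whatever Section 12.1 or 5.2 counts. Rescaling the marker does not alter the p-value for its slope, so the missing unit cannot change the primary test; the analyst will simply state the unit when reporting the odds ratio. Restating the basis of the calculation would make the section easier to follow but would leave the sample size, alpha, futility rule and conclusions as they are.
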